### 3.3.4 Withdrawal of patients from treatment or assessments

Patients may discontinue trial treatment or withdraw consent to trial participation as a whole (“withdrawal of consent”) with very different implications; please see [Section 3.3.4.1](#) and [3.3.4.2](#) below.

Every effort should be made to keep the patients in the trial, if possible, on treatment. Measures to control the withdrawal rate include careful patient selection, appropriate

explanation of the trial requirements and procedures prior to trial enrolment, as well as the explanation of the consequences of withdrawal. Patients should be made aware of potential anticipated GI side effects and investigators should provide guidance on how to avoid or overcome them.

The decision to discontinue trial treatment or withdraw consent to trial participation and the reason must be documented in the patient files and eCRF. If applicable, consider the requirements for Adverse Event collection reporting (please see [Section 5.2.6.2.1](#) and [5.2.6.2](#)).

### 3.3.4.1 Discontinuation of trial treatment

An individual patient will discontinue trial treatment if:

- The patient wants to discontinue trial treatment, without the need to justify the decision.
- An AE (CTCAE Grade 3 or higher) occurred, and the AE was assessed by the Investigator as related to the trial treatment ([Section 5.2.6.1.6](#) and [5.2.6.1.7](#)).
- A clinically significant laboratory change or abnormality occurred and the Investigator judges to warrant discontinuation of trial treatment.
- The patient develops a sinus tachycardia (HR >120/min in two consecutive measurements 5 minutes apart and/or tachyarrhythmia (HR >110/min) or cardiac condition requiring medical intervention.
- Ventricular tachycardia is seen on ECG or syncope.
- Clinically relevant changes are seen on the ECG (QTcF prolongation >500 ms or an increase of 60 ms from baseline (Visit 2), or Type Mobitz II, or third-degree AV block, or Torsade de Pointes) or the patient develops any symptomatic AV block, atrial fibrillation or atrial flutter requiring medical intervention.
- The patient develops a clinically relevant coronary artery disease (e.g., CCS grading of Angina pectoris grade III-IV, or congestive heart failure NYHA class III-IV, or any major adverse cardiovascular event)
- Signs of suicidal behaviour or ideation are detected.
- The patient develops a malignant neoplasm.
- The patient experiences systemic hypersensitivity. Refer to [Section 4.2.1](#).
- The patient develops a clinically significant elevation of liver enzymes. Refer to [Section 10.1](#).
- The patient experiences an infection with SARS-CoV-2 (as confirmed by RT-PCR test) and presents with signs or symptoms requiring discontinuation of trial treatment as per Investigator's discretion.
- The patient has repeatedly shown to be non-compliant with important trial procedures and, in the opinion of both, the Investigator and Sponsor representative, is not willing or able to adhere to the trial requirements in the future.
- The patient needs to take concomitant medication that interferes with the trial treatment for more than 2 weeks. Refer to [Section 4.2.2.1](#) and [4.2.2.2](#).
- The patient experiences tolerance issues with the dose due to AEs over 2 weeks within the treatment period before Visit 14 ([Section 4.1.2](#)).
- The patient is out of compliance with trial medication (missing doses), please see [Section 4.3](#).

The patient can no longer receive trial treatment for medical reasons (such as surgery, adverse events and other diseases not mentioned above, or pregnancy). If the patient becomes pregnant during the trial the trial medication must be stopped, the patient will be discontinued from the trial and followed up until birth or otherwise termination of the pregnancy. For further information, including the process for follow-up of the outcome of the pregnancy please see [Section 5.2.6.2.3](#).

If the trial treatment is permanently discontinued, the patient should undergo the procedures of the EOT and Follow-up visit (Visit 32 and 33 resp.) as outlined in the [Flow Chart](#) and [Section 6.2.3](#).

In case of a temporary reason, trial treatment should be restarted if it is possible from the compliance perspective and if medically justified, please refer to [Section 4.1.4](#).

Boehringer Ingelheim will closely monitor and medically review all adverse events CTCAE Grade 3 and higher.

If one of the following occurs:

- 1) three patients who were randomised to any of the three active treatment groups develop the same Grade 3 CTCAE adverse event\* assessed by the Investigator as related to the trial treatment;
- 2) two patients who were randomised to any of the three active treatment groups develop any Grade 4 CTCAE adverse event assessed by the Investigator related to the trial treatment;
- 3) one patient who was randomised to one of the three active treatment groups develops any Grade 5 CTCAE adverse event assessed by the Investigator related to the trial treatment.

Boehringer Ingelheim will pause the enrolment of new patients in the trial and, taking into consideration the DMC recommendations, discontinue the trial treatment for all patients, if needed.

\*For adverse events of nausea, vomiting, diarrhoea, constipation, or anorexia, hospitalization or prolongation of hospitalization caused by these respective events plus at least one of the following additional criteria specified below it is required to pause enrolment of new patients in the trial.

- Nausea: IV hydration; tube feeding, or total parenteral nutrition indicated
- Vomiting: IV hydration; tube feeding, or total parenteral nutrition indicated
- Diarrhoea: IV hydration; increase of  $\geq 7$  stools per day over baseline
- Constipation: obstipation with manual evacuation indicated
- Anorexia: IV hydration; tube feeding, or total parenteral nutrition indicated

Trial-specific procedures have been defined in case of increased liver enzymes after randomization. For details refer to [Section 10.1](#).

If new efficacy/safety information becomes available, Boehringer Ingelheim will review the benefit-risk-assessment and, if needed, pause or discontinue the trial treatment for all patients or take any other appropriate action to guarantee the safety of the trial patients.

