## 8.7 ADMINISTRATIVE STRUCTURE OF THE TRIAL

The trial is sponsored by Boehringer Ingelheim (BI).

A Coordinating Investigator is responsible to coordinate investigators at the different sites participating in this trial. Tasks and responsibilities are defined in a contract.

An independent external committee (Clinical Event Committee, [CEC]) will be established, jointly with trial 1404-0036 ([c31754142-02](#)), to adjudicate all cardiovascular, pancreatic, thyroid, and oncological trigger events identified by abnormal laboratory values and/ or adverse events. In order to assess the trigger events relevant source documents will be requested from investigators. They may include laboratory reports, reports from histology, ultrasound, CT, MRI or scintigraphy assessments, hospital discharge letters and medical reports from other physicians. The assessment will be blinded to treatment allocation. The process of identifying the events for adjudication and the adjudication process will be detailed in the CEC charter.

Data Monitoring Committee (DMC) will be established, jointly with trial 1404-0036 (c31754142-02). The DMC members are independent of BI, they are physicians experienced in the treatment of the disease under investigation and a statistician. The DMC will evaluate safety data and will receive urgent significant safety concerns, and cases of DILI, for immediate evaluation. While DMC members may be unblinded, measures are in place to ensure the blinding for everyone else involved in the trial. Regular DMC meetings will be held at specified intervals. The DMC will recommend continuation, modification, or termination of the trial. DMC recommendations as well as the final BI decision will be reported to the appropriate Regulatory Authorities (RAs)/Health Authorities (HAs), IRBs/ECs, and to investigators as requested by local law. Tasks and responsibilities of the DMC will be specified in the DMC charter.

Relevant documentation on the participating (Principal) investigators (e.g., their curricula vitae) will be filed in the ISF.

The investigators will have access to the BI web portal Clinergize to access documents provided by the Sponsor.

BI has appointed a Clinical Trial Leader (CT Leader), responsible for coordinating all required activities, in order to:

- manage the trial in accordance with applicable regulations and internal SOPs,
- direct the clinical trial team in the preparation, conduct, and reporting of the trial,

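### The first enrolment-pause trigger counts Grade 3 cases only, so under worst-grade counting the same related event at Grades 3, 3 and 4 forces no pause, while qualifying Grades 3, 3 and 3 does

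*Protocol*

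**What the plan says.** Protocol 3.3.4.1 lists three triggers, each limited to patients randomised to active treatment and to events that the investigator assessed as related:

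1. "three patients who were randomised to any of the three active treatment groups develop the same Grade 3 CTCAE adverse event"
2. "two patients who were randomised to any of the three active treatment groups develop any Grade 4 CTCAE adverse event"
3. one patient with any Grade 5 event.

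If one is met, the sponsor must pause enrolment. The further step, taken in the light of DMC recommendations, is conditional: "discontinue the trial treatment for all patients, if needed".

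An asterisk on the first trigger narrows it for nausea, vomiting, diarrhoea, constipation and anorexia. These lead to a pause only with "hospitalization or prolongation of hospitalization caused by these respective events plus at least one of the following additional criteria".

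Elsewhere the same section uses open-ended grades. An individual patient stops treatment when "An AE (CTCAE Grade 3 or higher) occurred" and was judged related. The sponsor "will closely monitor and medically review all adverse events CTCAE Grade 3 and higher".

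**The concern.** A safety trigger should not become easier to escape as cases become more severe. Read as written, a third case at Grade 4 instead of Grade 3 contributes to neither count: it is not a Grade 3 case for the first trigger, and alone it is one short for the second. A mandatory action then falls away because the third patient was worse off.

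At stake is whether the pause is automatic or left to judgement in that one pattern. Group-level triggers of this kind were added at a Health Authority's request (Protocol 11.1), so they should work without interpretation. No endpoint, estimate or error rate is involved.

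**Working it through.** The documents give no operating characteristic for this rule, so there is no figure to reproduce. The check is one of logic.

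**Inputs** (Protocol 3.3.4.1). Count active-arm patients once each, at worst grade, related events only:
- a = patients with the event in question at Grade 3 (meeting the asterisked criteria if it is one of the five listed terms)
- b = patients with that same event at Grade 4
- e = patients with some other related Grade 4 event
- c = patients with any related Grade 5 event

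**Rule as written:** pause if a ≥ 3, or b + e ≥ 2, or c ≥ 1.

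**Rule with *or higher* in the first trigger:** pause if a + b + (same-event Grade 5 cases) ≥ 3, or b + e ≥ 2, or c ≥ 1.

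**Three patients with the same event, no other events (e = 0).** Three patients and three grades give ten patterns:

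| Pattern | As written | With *or higher* |
|---|---|---|
| 3-3-3 | pause (a = 3) | pause |
| 3-3-4 | **no pause** (a = 2, b = 1, c = 0) | pause (2 + 1 = 3) |
| 3-4-4 | pause (b = 2) | pause |
| 4-4-4 | pause (b = 3) | pause |
| 3-3-5, 3-4-5, 3-5-5, 4-4-5, 4-5-5, 5-5-5 | pause (c ≥ 1) | pause |

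The rule as written fires in 9 of 10 patterns and the amended rule in 10 of 10. The count shows how narrow the gap is; the patterns are not equally likely, so 1 in 10 is not a risk.

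**How the gap ends.** From 3-3-4, the rule as written fires after any one of these:
- one more qualifying Grade 3 case of that event (a = 3)
- a related Grade 4 event of any kind in a second patient (b + e = 2)
- any related Grade 5 event (c = 1)

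The effect is therefore a missing or delayed pause, and it also requires that no other related Grade 4 event has occurred in the active arms.

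**Counting convention.** The protocol states none. If a patient whose event was Grade 3 before it became Grade 4 also counts under the first trigger, then a = 3 and the pause applies. Only a case first seen at Grade 4 then leaves a = 2.

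**Can a probability be given?** Not from the documents.
- Protocol 1.2 reports severe events in 3 of 67 treated patients in the multiple rising dose trial (3/67 = 4.5%): two diarrhoea, one vomiting, with no serious adverse events. Both terms carry the asterisk, and hospitalisation would have made them serious (Protocol 5.2.6.1.2), so none of the three would have counted under the first trigger.
- The same section says that the single rising dose trial stopped early for severe nausea and vomiting, without a count.
- Neither source gives a rate of related Grade 3 or Grade 4 events by term.

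**Timing.** Protocol 11.4 (August 2022) describes recruitment as in its final stage. The current protocol is dated 27 July 2023. The SAP history table records the transfer of second screening readings for China on 18 December 2023, and Protocol 7.2.6 places these re-readings at the end of the trial. Counting back 48 weeks (336 days) from 18 December 2023 gives 16 January 2023. This suggests that enrolment had closed by about then, but it is an inference, as no closing date is stated.

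**The case against.** The strongest objection is that the result depends on a counting rule that the protocol does not contain. On a natural reading, a patient whose event reached Grade 3 and then Grade 4 did develop it at Grade 3, and the pause follows. That stands, and the conclusion is conditional for this reason. It does not remove the gap for a case first seen at Grade 4. The contrast with the open-ended wording elsewhere in the section also gives a reader grounds to exclude Grade 4 cases from the first trigger.

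Second, the DMC charter is not available. Protocol 4.1.5.1 refers to it for unblinded DMC assessment of events that may lead to trial discontinuation, so it may settle the counting. That limits the claim to the protocol text.

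Third, the only mandatory action is an enrolment pause, and it probably had no remaining effect by the current version. That also stands, as an inference.

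A reader might go further and infer that a worse signal would go unhandled. The documents do not support this. All three patients stop treatment. The sponsor reviews every event of Grade 3 and above and, on new efficacy or safety information, "will review the benefit-risk-assessment and, if needed, pause or discontinue the trial treatment for all patients". Protocol 8.7 adds: "The DMC will evaluate safety data and will receive urgent significant safety concerns, and cases of DILI, for immediate evaluation". The DMC also sees unblinded safety data at regular intervals (Protocol 3.2). Nor does the gap prevent a stop for everyone, because that step is discretionary even when a trigger is met.

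**Conclusion.** The wording gap is real and its consequence is very small. Under worst-grade counting, one three-patient pattern (3-3-4 of the same related event, with no other related Grade 4 and no related Grade 5 event) escapes a pause that qualifying 3-3-3 would force. If passing through Grade 3 counts, only a case first seen at Grade 4 escapes. Nothing suggests that the reversal is intended: in every other three-patient pattern, greater severity keeps the trigger.

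The conclusion rests on the literal text of Protocol 3.3.4.1, the unstated counting convention, and no contrary rule in the unseen charter. No likelihood can be attached to the pattern, because any figure would come from assumed event rates. The point does not touch the trial's efficacy or safety analyses.

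**What to change.** - Extend the first trigger of Protocol 3.3.4.1 to the same related event at Grade 3 *or higher*, and state that each patient counts once.
- Keep the asterisked criteria for Grade 3 cases of the five listed terms, and say whether they also apply to a Grade 4 case counted under this trigger.
- If the DMC charter repeats the rule, use the same wording there. Protocol 11.3 says that the stopping rules were aligned with another trial of the compound, so check that text too.

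The cost is a few words and a slightly higher chance of an enrolment pause. A separate amendment is not warranted: changes need ethics committee and authority approval (Protocol 8.1), and about 180 sites are planned (Protocol 3.3). The edit can go into any amendment made for another reason.

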#### 3.3.4.2 Withdrawal of consent to trial participation

Patients may withdraw their consent to trial participation at any time without the need to justify the decision.

If a patient wants to withdraw consent, the Investigator should be involved in the discussion with the patient and explain the difference between trial treatment discontinuation and withdrawal of consent to trial participation, as well as explain the options for continued follow-up after trial treatment discontinuation, please see [Section 3.3.4.1](#) above.

#### 3.3.4.3 Discontinuation of the trial by the Sponsor

Boehringer Ingelheim reserves the right to discontinue the trial overall or at a particular trial site at any time for the following reasons:

1. Failure to meet expected enrolment goals overall or at a particular trial site.
2. New efficacy or safety information invalidating the earlier positive benefit-risk-assessment, please see Section 3.3.4.1.
3. Deviations from GCP, the trial protocol, or the contract impairing the appropriate conduct of the trial.

Further follow up of patients affected will occur as described in Section 3.3.4.1.

The Investigator/ the trial site will be reimbursed for reasonable expenses incurred in case of trial termination (except in case of the third reason).

## 4. TREATMENTS

### 4.1 INVESTIGATIONAL TREATMENTS

#### 4.1.1 Identity of the Investigational Medicinal Products

Table 4.1.1:1 Test product

Substance:	BI 456906
Pharmaceutical formulation:	Solution for injection
Source:	Boehringer Ingelheim Pharma GmbH & Co. KG, Germany
Unit strength:	BI 456906 0.6 mg/mL, 1.8 mg/mL, 3.6 mg/mL, 4.8 mg/mL, 6.0 mg/mL Pre-filled syringes, 0.5 mL fill volume
Posology:	One dose weekly (two pre-filled syringes)
Mode of administration:	s.c. injection

Table 4.1.1:2 Reference product

Substance:	Placebo to match BI 456906
Pharmaceutical formulation:	Solution for injection
Source:	Boehringer Ingelheim Pharma GmbH & Co. KG, Germany
Unit strength:	Placebo to match BI 456906 Pre-filled syringes, 0.5 mL fill volume
Posology:	One dose weekly (two pre-filled syringes)
Mode of administration:	s.c. injection

#### 4.1.2 Selection of doses in the trial and dose modifications

For this trial, target maintenance doses of 2.4 mg, 4.8 mg and 6.0 mg once weekly dosing were selected based on the following considerations:

Safety and tolerability of BI 456906 is being evaluated in healthy volunteers with obesity or overweight up to 6 weeks for doses ranging from 0.7 to 3.15 mg/ week (daily administration)

and 0.3 to 3.0 mg/ week (weekly administration) and up to 16 weeks for doses ranging from 0.6 to 4.8 mg/ week (once or twice weekly administration) in trial 1404-0003 ([c21168858-05](#)). The first part of the trial with the treatment duration up to 6 weeks has already been completed. The available clinical data indicate that the estimated human dose for maintenance in obesity might be reached with 4.8 mg/ week to achieve the anticipated exposure.

The safety margin for the 4.8 mg/ week dose has an exposure multiple of 5.3 fold ( $C_{max,ss}$ ) and 4.1 fold ( $AUC_{\tau,ss}$ ) to the no-observed-adverse-effect level in mice and cynomolgus monkeys.

However, pre-clinical models showed that higher exposures than in obesity might be needed in NASH to show meaningful efficacy ([n00254747-01](#) and [n00267699-01](#)). This is potentially based on the effect of the GCGR agonism which is assumed to increase directly the lipid and fatty acid oxidation in the liver. The effect of the GCGR agonism is anticipated to be more pronounced at higher doses. Since this trial is intended to be a dose-finding trial, 6.0 mg/ week dose was selected.

The safety margin for the 6.0 mg/ week dose has an exposure multiple of 3.1 fold ( $C_{max,ss}$ ) and 3.1 fold ( $AUC_{\tau,ss}$ ) to the no-observed-adverse-effect level of the 26-week toxicological study in mice. Safety margins to the no-observed-adverse-effect level of the 39-week toxicological study of 2.4 and 0.8 based on  $C_{max}$  and 2.6 and 0.7 based on AUC were derived for male and female cynomolgus monkeys, respectively. These calculations are based on a population PK model, set up with PK data from trial 1404-0001 ([c22991258-01](#)) and 1404-0003 ([c21168858-05](#)). It should be noted that the expected  $C_{max}$  and AUC refer to the enrolment criteria (70 kg and BMI 25 kg/m^2) and is hence a worst-case scenario. A heavier individual will have lower  $C_{max}$  and AUC.

The NOAEL for BI 456906 in cynomolgus monkeys is only limited by the effect on body weight loss which reflects the pharmacology of the compound. Obviously, especially female monkeys with a profound lower initial body weight than male monkeys have to be considered oversensitive.

The lowest dose of 2.4 mg/ week in this trial is predicted to achieve sub-therapeutic PD response comparable to placebo in patients with NASH and fibrosis, however, still providing weight loss and improvement in the metabolic status.

The results from the 1404-0003 indicate that the most common GI adverse events such as nausea and vomiting occur at the beginning of the drug exposure and can be mitigated by a careful dose escalation. The tolerability of GLP-1 receptor agonists is known to improve over time, so is assumed that even higher doses of BI 456906 will be tolerated [[R20-0479](#)]. In addition, close monitoring is implemented in this trial to assure patients' safety.

Overall, the three selected maintenance doses are anticipated to support robust dose-exposure-response analyses for multiple safety and efficacy measures to serve as a basis for selection of the suitable dose regimen for the phase III trial.

Selected doses cover a safe starting dose of 0.3 mg/ week with different dose escalation schemes up to the target maintenance dose. The first 10 weeks of the dose escalation period will be identical for all three active treatment groups. The duration of the dose escalation up to the target maintenance dose differs among the active treatment groups from 14 to 22 weeks.

Dose adjustment will be allowed in all groups during the dose escalation period after Visit 14 as well as any time during the maintenance period based on the occurrence of AEs. If a patient does not tolerate a dose due to AEs in the previous two weeks and wishes to reduce the dose, then the dose should be decreased to the next lower tolerated target maintenance dose. The assignment of the lower dose will occur in a blinded fashion via IRT.

Examples:

- If a patient who does not tolerate a dose of 2.4 mg over two weeks during the dose escalation period and wishes to reduce the dose will be changed to placebo;
- If a patient who does not tolerate a dose of 3.6 mg over two weeks during the dose escalation period and wishes to reduce the dose will be changed to 2.4 mg;
- If a patient who does not tolerate a dose of 4.8 mg over two weeks during the maintenance period and wishes to reduce the dose will be changed to 2.4 mg.

Dose adjustment should be done at the site. A patient is allowed to adjust the dose two times during the entire treatment period, once during the dose escalation and once during the maintenance period.

